Non Interventional Study Protocol Amendment

BI Study No.:	1160.139	
BI Investigational Product(s):	Dabigatran etexilate mesilate	
Title:	A regulatory requirement non-interventional study to monitor the safety and effectiveness of Pradaxa (Dabigatran etexilate mesilate, 110 mg or 150 mg b.i.d.) in Korean patients with non-valvular atrial fibrillation (SPARK: Safety study of Pradaxa in AF patients by Regulatory requirement of Korea)	
Clinical Phase:	IV	
Trial Clinical Monitor:	[REDACTED] [REDACTED] [REDACTED] [REDACTED] [REDACTED] [REDACTED] Phone [REDACTED] Fax: [REDACTED]	
Principal Investigator:	Not applicable	
Status:	Final protocol amendment IV	
Version and Date:	Version: 4.0	Date: 10 June 2013
Page 1 of 42		
Proprietary confidential information.		
© 2014 Boehringer Ingelheim International GmbH or one or more of its affiliated companies. All rights reserved.		
This document may not - in full or in part - be passed on, reproduced, published or otherwise used without prior written permission.		

Proprietary confidential information. © 2014 Boehringer Ingelheim International GmbH or one or more of its affiliated companies.

NON-INTERVENTIONAL STUDY PROTOCOL SYNOPSIS

Name of company/Marketing Authorisation Holder: Boehringer Ingelheim Korea		Tabulated Study Protocol	
Name of finished product: Pradaxa			
Name of active ingredient: Dabigatran etexilate mesilate			
Protocol date: 29 April 2011	Trial number: 1160.139		Revision date: 10 June 2013
Title of study: A regulatory requirement non-interventional study to monitor the safety and effectiveness of Pradaxa (Dabigatran etexilate mesilate, 110 mg or 150 mg b.i.d.) in Korean patients with non-valvular atrial fibrillation (SPARK: Safety study of Pradaxa in AF patients by Regulatory requirement of Korea)			
Principal Investigator: Not Applicable			
Study site(s) : Multi-centre study			
Clinical phase: IV			
Objectives: To monitor the safety profile and effectiveness of dabigatran etexilate mesilate in patients with non-valvular atrial fibrillation in a routine clinical practice setting			
Methodology: Prospective, non-interventional, open-label, multi-centre national study			
No. of patients: Total entered: 3,000 approximately No. of patients for short-term surveillance: 1,500 No. of patients for long-term surveillance: 1,500 each treatment: Single arm (N=3,000 approximately)			
Diagnosis: Patients diagnosed with non-valvular atrial fibrillation and at risk of stroke or systemic embolism			
Main criteria for inclusion: 1) Age \geq 18 years at enrollment 2) Patients who have been started on Pradaxa in accordance with the approved label in Korea 3) Patients who have signed on the data release consent form			

Proprietary confidential information. © 2014 Boehringer Ingelheim International GmbH or one or more of its affiliated companies.

Name of company/Marketing Authorisation Holder:		Tabulated Study Protocol	
Boehringer Ingelheim Korea			
Name of finished product:			
Pradaxa			
Name of active ingredient:			
Dabigatran etexilate mesilate			
Main criteria for exclusion:	1) Patients with previous exposure to Pradaxa 2) Clinically significant bleeding 3) Increased risk of bleeding due to following diseases; Recent gastrointestinal ulceration Recent intracranial or intracerebral bleeding history Intraspinal or intracerebral vascular abnormalities Recent brain, spinal or ophthalmic surgery Recent brain or spinal injury Known or suspected oesophageal varices Arteriovenous malformations Vascular aneurysms Presence of malignant neoplasms at high risk of bleeding 4) Concomitant treatment with any other anticoagulants e.g. unfractionated heparin (UFH), low molecular weight heparins (enoxaparin, dalteparin etc), heparin derivatives (fondaparinux etc), oral anticoagulants (warfarin, rivaroxaban, apixaban etc) except under the circumstances of switching therapy to or from Pradaxa or when UFH is given at doses necessary to maintain an open central venous or arterial catheter 5) Severe renal impairment (CrCl < 30mL/min) 6) Concomitant treatment with oral ketoconazole or dronedarone 7) Patients hypersensitive to dabigatran or dabigatran etexilate or to any ingredient in the formulation 8) Prosthetic heart valve replacement 9) No creatinine clearance collected within at least one year prior to enrollment 10) Current participation in other clinical trials		
	Dabigatran etexilate mesilate		
dose:	110 mg b.i.d., 150 mg b.i.d.		
mode of admin. :	Oral administration		
Comparator product(s): Not applicable			
dose:			
mode of admin. :			

Proprietary confidential information. © 2014 Boehringer Ingelheim International GmbH or one or more of its affiliated companies.

Name of company/Marketing Authorisation Holder:		Tabulated Study Protocol	
Boehringer Ingelheim Korea			
Name of finished product:			
Pradaxa			
Name of active ingredient:			
Dabigatran etexilate mesilate			
Protocol date: 29 April 2011	Trial number: 1160.139		Revision date: 10 June 2013
Duration of treatment:	1) Treatment duration for short-term surveillance: 12±2 weeks, long-term surveillance: 24±2 weeks 2) Study duration: 6 years (Study period required by the Ministry of Food and Drug Safety (MFDS) is from 18 Feb 2011 to 17 Feb 2017. Interim reports are expected biannually for the initial two years and annually thereafter by May 2017.)		
Criteria for effectiveness:	Incidence of stroke or systemic embolism		
Criteria for safety:	All reported adverse events in patients who have taken at least one dose of Pradaxa will be noted.		
Statistical methods:	Descriptive statistics		

Proprietary confidential information. © 2014 Boehringer Ingelheim International GmbH or one or more of its affiliated companies.

FLOW CHART

Data points	Baseline	Follow-up 1(Short-term)	Follow-up 2(Long-term)
Visit Number	1	2	3
Week/s	0	12±2	24±2
Diagnosis	X		
Inclusion / exclusion criteria	X		
Demographics	X		
Renal Function	X		
Lifestyle factors	X		
AF disease characteristics	X		
Medical history	X		
Anti-thrombotic therapy	X	X	X
Concomitant medications	X	X	X
Pradaxa administration status	X	X	X
Vital signs	X	X	X
Effectiveness endpoints		X	X
Changes in lab tests together with action on drugs		X	X
Adverse events		X	X
Treatment compliance		X	X
Study completion		X	X

Proprietary confidential information. © 2014 Boehringer Ingelheim International GmbH or one or more of its affiliated companies.

TABLE OF CONTENTS

TITLE PAGE	1
NON-INTERVENTIONAL STUDY PROTOCOL SYNOPSIS	2
FLOW CHART	5
TABLE OF CONTENTS	6
ABBREVIATIONS	9
1. INTRODUCTION.....	10
1.1 MEDICAL BACKGROUND.....	10
1.2 DRUG PROFILE	11
2. RATIONALE, OBJECTIVES, AND BENEFIT-RISK ASSESSMENT	12
2.1 RATIONALE FOR PERFORMING THE STUDY	12
2.2 STUDY OBJECTIVES.....	12
2.2.1 Primary objective	12
2.2.2 Secondary objective	12
2.3 BENEFIT-RISK ASSESSMENT	12
3. DESCRIPTION OF DESIGN AND STUDY POPULATION	13
3.1 OVERALL DESIGN AND PLAN	13
3.1.1 Administrative structure of the study	13
3.2 DISCUSSION OF STUDY DESIGN.....	13
3.3 SELECTION OF POPULATION	14
3.3.1 Main diagnosis for study entry	14
3.3.2 Inclusion criteria	14
3.3.3 Exclusion criteria	14
3.3.4 Removal of patients from therapy or assessments.....	15
3.3.4.1 Removal of individual patients (therapy or assessments)	15
3.3.4.2 Discontinuation of the study by the sponsor	15
4. TREATMENTS.....	16
4.1 PRESCRIBED TREATMENTS TO BE OBSERVED.....	16
4.1.1 Identity of the product(s).....	16
4.1.2 Method of assigning patients to treatment groups	16

10.4 SAE REPORT FORM.....	41
10.5 PREGNANCY MONITORING FORM	41
10.6 PRODUCT LOCAL LABEL.....	41
10.7 SPECIAL PRECAUTIONS FOR USE_RISK OF BLEEDING	41
11. SUMMARY OF NIS STUDY PROTOCOL MODIFICATIONS.....	42

Proprietary confidential information. © 2014 Boehringer Ingelheim International GmbH or one or more of its affiliated companies.

ABBREVIATIONS

AE	Adverse Event
AF	Atrial Fibrillation
aPTT	Activated Partial Thromboplastin Time
ASA	Acetyl Salicylic Acid
CA	Competency Authority
CABG	Coronary Artery Bypass Graft
CHF	Congestive Heart Failure
CK-MB	Creatinine Kinase-Myocardial Band
CML	Clinical Monitor Local
CRF	Case Report Form
CRO	Contract Research Organization
CSO	Clinical Safety Officer
CT	Computed Tomography
eCRF	Electronic Case Report Form
ECG	Electrocardiograph
EDC	Electronic Data Capture
FU	Follow up
KIMS	Korea Index of Medical Specialties
KPAC	Korean Pharmaceutical Affairs Code
KPMA	Korea Pharmaceutical Manufacturers Association
KRPIA	Korean Research-based Pharmaceutical Industry Association
GCP	Good Clinical Practice
LVD	Left Ventricular Dysfunction
ICH	International Conference on Harmonisation of Technical Requirements for Registration of Pharmaceuticals for Human Use
ID	Identification
IEC	Independent Ethics Committee
INR	International Normalized Ratio
IRB	Institutional Review Board
MedDRA	Medical Dictionary for Drug Regulatory Activities
MFDS	The Ministry of Food and Drug Safety
MR	Magnetic Resonance
mRS	Modified Rankin Scale
NCE	New Chemical Entity
NIS	Non-Interventional Study
PCI	Percutaneous Coronary Intervention
PMS	Post Marketing Surveillance study
SAE	Serious Adverse Event
TIA	Transient Ischemic Attack
TSAP	Trial Statistical Analysis Plan
ULN	Upper Level of Normal
VKA	Vitamin K antagonist

1. INTRODUCTION

1.1 MEDICAL BACKGROUND

Atrial fibrillation (AF) is the most common cardiac arrhythmia seen in the community and affects approximately 12% of population (R03-1233). It is estimated that 6 million people in Europe and 2.7 million people in the USA suffer from AF (P10-10141, P06-08196). The lifetime risk for the development of AF is one in four for those over the age of 40 years (R09-4884). In Korea, the number of patients visited hospital for AF or atrial flutter was 80,000, approximately, according to the 2009 National Health Insurance Statistical Yearbook.¹ On average, the number of patients diagnosed with AF between 2001~2004 was 52,025 and AF prevalence in the age over 60 and over 70 was 1.95% and 2.41%, respectively, according to the KORAF (KOREan Atrial Fibrillation Registry).²

The prevalence of AF rises with advancing age, increasing from less than 1% in those under 60 years of age to nearly 20% in those aged 85 years or more (R09-4875). The overall prevalence of AF in hospital setting is also increasing; hospital admissions due to AF have increased by 60% over the past 20 years (R10-1345). Furthermore, the prevalence of AF is estimated to double by 2050 due to the aging of the world's population (R03-1233).

Thromboembolic complications, particularly strokes, are a major cause of morbidity and mortality in patients with AF. Most of the strokes associated with AF are due to distal embolization of a left atrial thrombus, particularly arising from the left atrial appendage. Patients with AF have a four to five fold higher risk of stroke than those without AF (R96-0252, R03-1241). Furthermore, approximately 15% of all strokes are directly attributed to AF and patients with strokes associated with AF have worse outcome with higher mortality than those with strokes not associated with AF (R09-4892).

The risk of stroke or systemic embolism in patients with AF is influenced by other vascular risk factors including the history of previous strokes or transient ischemic attacks (TIA), hypertension, left ventricular dysfunction (LVD), congestive heart failure (CHF), advanced age, diabetes mellitus, and coronary artery disease. Patients without any of these risk factors, i.e., lone AF, have a lower likelihood for the occurrence of stroke, thromboembolic events and stroke-related mortality (R03-1229, P06-08196, and R03-1241). The classic CHADS₂ (Congestive heart failure, Hypertension, Age > 75, Diabetes, prior Stroke/transient ischemic attack, see Appendix 10.1) score is a risk score that was developed as a simple method for clinicians to assess the risk of stroke and thromboembolism in patients with AF (P06-10925). Given that the CHADS₂ score does not include many stroke-related risk factors, a modification has been developed (CHA₂DS₂-VASc score, see Appendix 10.1) to improve its predictive value of stroke and thromboembolic events (R10-5332, P10-10141).

Strokes due to AF are partly preventable by antithrombotic therapy. A meta-analysis of controlled clinical trials demonstrated that warfarin decreased the risk of stroke/systemic embolism, on average, by 62% versus placebo, while antiplatelet therapy reduced the occurrence of stroke by 22% compared to placebo. However when the analysis was confined to aspirin only trials, aspirin reduced stroke by a non-significant 19% (95% CI: -1% to 35%)

Proprietary confidential information. © 2014 Boehringer Ingelheim International GmbH or one or more of its affiliated companies.

compared to placebo (P07-07953, R03-1227). Oral anticoagulation with vitamin K antagonists (VKAs, e.g. warfarin) is the current standard therapy for stroke prevention in AF patients with moderate to high-risk of stroke (P10-10141, P07-04925, P06-08196, P10-00811). However, VKAs have clinically important limitations including a narrow therapeutic window, an unpredictable dose-response effect, numerous drug-drug and drug-food interactions, and slow onset and offset of action. As a result, many patients with AF do not receive VKAs and instead receive ASA, antiplatelet agents, both or no antithrombotic therapy (R03-1241). Even when VKAs are used, regular anticoagulation monitoring and dose adjustments are needed to achieve effective anticoagulation.

In a real-life setting, VKA treatment often results in INR (International Normalized Ratio) values outside of the target therapeutic range (R10-0768, R09-1522), leaving patients at increased risk of either stroke or bleeding. Due to the clinical and practical limitations of VKAs, multiple new oral anticoagulants are in clinical development including, mainly, direct thrombin inhibitors and factor Xa inhibitors (P07-08370). Pradaxa (dabigatran etexilate mesilate), a direct thrombin inhibitor, has been approved for the risk reduction of stroke or systemic embolism in patients with AF since February 2011, in Korea. In a clinical trial involving 118,113 patients, compared to warfarin, dabigatran etexilate mesilate (150 mg b.i.d.) reduced the occurrence of stroke (both ischemic and hemorrhagic) and systemic embolism significantly, while the rate of major bleeding was similar with both treatment. RE-LY (P09-11669). Furthermore, dabigatran etexilate mesilate (110 mg b.i.d.) was found to be non-inferior to warfarin for the prevention of stroke or systemic embolism while resulting in fewer major bleeds. Importantly, both doses of dabigatran etexilate mesilate were associated with significantly reduced occurrence of intracranial haemorrhage compared to warfarin (P09-11669).

1.2 DRUG PROFILE

Dabigatran etexilate mesilate is the orally bioavailable prodrug of dabigatran, a novel, synthetic, direct thrombin inhibitor. Dabigatran etexilate mesilate itself does not have any antithrombin activity. Following oral administration it is rapidly converted via serum esterase to the active moiety, dabigatran, which is a non-peptidic, potent, competitive, and reversible inhibitor of thrombin. (U98-3208)

2. RATIONALE, OBJECTIVES, AND BENEFIT-RISK ASSESSMENT

2.1 RATIONALE FOR PERFORMING THE STUDY

According to the local regulations, when a new chemical entity (NCE) is registered, a post marketing surveillance study (NIS) of an extended period (4 or 6 years) should be conducted. Such NIS can provide supplementary data to monitor the safety of NCEs in a real-life situation. Data collected in randomised clinical trials with strict inclusion/exclusion criteria and rigorous monitoring schemes have limitations.

This is a prospective, non-interventional, open-label, multi-centre study. It will provide additional safety information of Pradaxa in Korean patients with non-valvular AF in clinical settings.

2.2 STUDY OBJECTIVES

2.2.1 Primary objective

The primary objective of this study is to monitor the safety profile of Pradaxa in Korean patients with non-valvular AF in a routine clinical setting.

2.2.2 Secondary objective

The secondary objective of the study is to monitor the effectiveness of Pradaxa in reducing the risk of stroke or systemic embolism in Korean patients with non-valvular AF, by observing the incidence of stroke or systemic embolism.

2.3 BENEFIT-RISK ASSESSMENT

Patients will be managed according to the local practice guidelines. The choice of treatment will be solely at the discretion of the participating physician. Pradaxa will be administered according to the approved label in Korea. Hence there are no additional risks to patients by participating in this NIS.

3. DESCRIPTION OF DESIGN AND STUDY POPULATION

3.1 OVERALL DESIGN AND PLAN

This NIS is a prospective, non-interventional, open-label, multi-centre study. As per regulation, the re-examination period extends from 18 Feb 2011 until 17 Feb 2017 (6 years). However, active enrolment is to be initiated in 2012 after finalizing the re-imbursement agreement with the authority. Before initiation of the study, any newly reported adverse events will be closely monitored. The last patient follow up is expected in 2015.

3.1.1 Administrative structure of the study

This study will be managed by a project manager of Boehringer Ingelheim Korea. Data management and statistics will be outsourced to a qualified contract research organization (CRO).

3.2 DISCUSSION OF STUDY DESIGN

This is a single arm study with dabigatran etexilate mesilate cohort.

Loss to follow up

All efforts will be made to minimize loss to follow up, particularly in the tracking of lost patients. To the extent possible, vital status, at minimum, for patients lost to follow up will be obtained. This allows assessing the impact of informative censoring due to treatment discontinuation. Also, patients lost to follow up will be characterized compared to the remaining patients and reason and time point of loss to follow up will be evaluated.

Channeling bias

Channeling bias can occur due to preferential prescribing in relation to different risks for the events of interest: e.g., if dabigatran would be more often prescribed to higher risk patients compared to other treatments, higher incidences of outcome events were then expected in the dabigatran group.

Information and recall bias

Information bias can e.g. occur due to selective reporting of already established and known adverse effects for a known product as compared to a new product (dabigatran), or vice versa. A standardized data collection form will be used for assessing exposure and AEs. These standardized procedures for data collection are intended to minimize such biases. Recall bias may be caused, e.g. if visits are separated by long time intervals and patient forget certain information. It can be reduced by associating questions with specified time intervals (e.g. how often did you take this co-medication *during the last 5 days*).

Proprietary confidential information. © 2014 Boehringer Ingelheim International GmbH or one or more of its affiliated companies.

Confounding

As in any observational study, confounding may affect the estimation of association between drug exposure and outcome of interest and statistical techniques. However, as only major confounders for selected research questions can be captured, residual (unmeasured) confounding may remain.

3.3 SELECTION OF POPULATION

Minimum 3,000 patients will be enrolled at approximately 40 sites by as many as 80 or more investigators. The treating physicians will mainly be cardiologists or neurologists. To minimize the selection bias, consecutive patients from each site who meet inclusion criteria will be enrolled in this study.

3.3.1 Main diagnosis for study entry

Patients diagnosed with non-valvular AF and at risk of stroke or systemic embolism will be included. Physician should carefully review the product label in Korea before prescribing Pradaxa to patients (Attachment 4). Updated label information is found in eCRF and ISF (Investigator Site File). **The exclusion criteria reflect the contraindication of the product label. Thus if the contraindication section of the label is updated, the physician should follow the up-to-date prescribing information ahead of the inclusion / exclusion criteria of this protocol.**

3.3.2 Inclusion criteria

- **Age \geq 18 years at enrollment**
- Patients who have been started on Pradaxa in accordance with the approved label in Korea
- Patient who has signed on the data release consent form

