3.3.3 Exclusion criteria

- Patients with previous exposure to Pradaxa
- Clinically significant bleeding
- **Increased risk of bleeding due to following diseases;**
Recent gastrointestinal ulceration
Recent intracranial or intracerebral bleeding history
Intraspinal or intracerebral vascular abnormalities
Recent brain, spinal or ophthalmic surgery

Proprietary confidential information. © 2014 Boehringer Ingelheim International GmbH or one or more of its affiliated companies.

Recent brain or spinal injury

Known or suspected oesophageal varices

Arteriovenous malformations

Vascular aneurysms

Presence of malignant neoplasms at high risk of bleeding

- Concomitant treatment with any other anticoagulants e.g. unfractionated heparin (UFH), low molecular weight heparins (enoxaparin, dalteparin etc), heparin derivatives (fondaparinux etc), oral anticoagulants (warfarin, rivaroxaban, apixaban etc) except under the circumstances of switching therapy to or from Pradaxa or when UFH is given at doses necessary to maintain an open central venous or arterial catheter
- Severe renal impairment ($\text{CrCl} < 30\text{mL/min}$)
- Concomitant treatment with oral ketoconazole **or dronedarone**
- Patients hypersensitive to dabigatran or dabigatran etexilate or to any ingredient in the formulation
- Prosthetic heart valve replacement
- No creatine clearance collected within at least one year prior to enrollment
- Current participation in other clinical trials

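### Do the entry criteria contradict each other on prior Pradaxa use, and does the unstated gap between first dose and Visit 1 bias the safety results?

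*Combined protocol and SAP*

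**What the plan says.** Section 3.3.2 takes "Patients who have been started on Pradaxa in accordance with the approved label in Korea". Section 3.3.3 removes "Patients with previous exposure to Pradaxa" and, separately, "Clinically significant bleeding". None of the three carries a date, although the age and creatinine clearance criteria in the same lists are dated to enrolment.

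Section 6.2.2.1 ties Visit 1 to enrolment, and Sections 6.2.2.2 and 6.2.2.3 count the later visits from Visit 1. Section 5.2.2.2 collects adverse events from the start of treatment. Section 5.1.2 defines the effectiveness set by time on drug. The one-month look-back for other medication runs from Pradaxa initiation in Section 4.2 and from the baseline visit in Section 6.2.2.1.

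The synopsis gives "Treatment duration for short-term surveillance: 12±2 weeks, long-term surveillance: 24±2 weeks". Section 3.3.1 says that the exclusions mirror the label's contraindications and that "Physician should carefully review the product label in Korea before prescribing Pradaxa to patients".

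On timing, Section 1.1 says the drug "has been approved for the risk reduction of stroke or systemic embolism in patients with AF since February 2011, in Korea". Section 3.1 adds "However, active enrolment is to be initiated in 2012 after finalizing the re-imbursement agreement with the authority" and "Before initiation of the study, any newly reported adverse events will be closely monitored".

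**The concern.** Measured at enrolment, a patient who has already started the drug has been exposed to it, so the inclusion criterion and the first exclusion seem to cancel out. If previous exposure instead means an earlier course, the conflict goes, but nothing limits how long a patient may have been on drug before Visit 1.

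A long lag would matter because safety is the primary objective (Section 2.2.1). A patient who died or stopped attending between first dose and Visit 1 would probably never be enrolled. A patient who bled early could be turned away under the undated bleeding exclusion. Back-collection of adverse events and the all-treated safety set reach enrolled patients only. Early harm could then be understated.

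The calendar makes a lag imaginable: from 18 February 2011, the start of the re-examination period, to 1 January 2012 is 317 days, about 45 weeks, during which patients could have started treatment outside the study.

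**Working it through.** The plan states no figure on this point, so there is none to reproduce. The check is to read the sections together and then see how large the effect could be.

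**1. The two criteria.** There are three readings.
- Previous means at any time before enrolment: every patient who has started is excluded, and the study has no eligible patients. No site could apply this.
- Previous means before the present course: the criteria select new users.
- The drug is prescribed at Visit 1: the criteria again select new users.

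Only the last two can be used, and they agree on the population.

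**2. Does the rest of the protocol fit a start at or near Visit 1?**
- The flow chart labels baseline week 0. Adverse events, compliance, effectiveness and laboratory changes have no entry at that visit, as expected if there is no earlier time on drug.
- The synopsis gives treatment durations equal to the visit schedule, and Section 6.2.2 calls follow-up a treatment period of the same length.
- In Section 6.2.2.1 the patient is asked at Visit 1 to report events that appear once treatment begins. The dose is recorded there, and Visit 2 records changes to it.
- Section 3.3.1 makes the exclusions label contraindications and puts the label review ahead of prescribing. Bleeding is therefore judged when the drug is prescribed, and a later bleed is an adverse event under Section 5.2.2.2.

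On this reading the different anchors (initiation, baseline, start of treatment, Visit 1) are the same day or close to it.

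**3. Would a long lag fit the stated duration?** Time on drug at Visit 2 is the lag L plus the visit week. For L = 4 weeks, an on-time visit falls at 4 + 12 = 16 weeks, outside 12 ± 2. Only a visit at week 10 fits (4 + 10 = 14). For L = 2 weeks, an on-time visit falls at 14 weeks, the edge of the window.

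**4. Size if sites did enrol late.** All inputs here are assumptions: p is the share enrolled late, L the lag in weeks, F the follow-up in weeks. The figures apply only to events that prevent enrolment.

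(a) Constant hazard, counted from Visit 1: 0% at any L.

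(b) Constant hazard, person-time from first dose. Understatement = pL / (pL + F).

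| F | p | L | Result |
|---|---|---|---|
| 12 | 25% | 2 | 0.5/12.5 = 4.0% |
| 12 | 25% | 4 | 1/13 = 7.7% |
| 12 | 100% | 2 | 2/14 = 14.3% |
| 12 | 100% | 4 | 4/16 = 25% |
| 24 | 25% | 4 | 1/25 = 4.0% |
| 24 | 100% | 4 | 4/28 = 14.3% |

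(c) Hazard doubled in weeks 0 to 4, counted from Visit 1, F = 12. Full risk = 4×2 + 8 = 16 units. With L = 2 it is 2×2 + 10 = 14, a deficit of 12.5%; with L = 4 it is 12, a deficit of 25%. At p = 25% these become 3.1% and 6.2%.

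(d) Stress case: everyone enrolled 2 weeks late, 12-week risk of stopping or death 10%, Weibull hazard. H = −ln(0.9) = 0.1054. Risk before Visit 1 = 1 − exp(−H(2/12)^k).
- k = 1: 0.0174, or 52 per 3,000 starters. The 12-week risk seen from Visit 1 stays at 10.0%.
- k = 0.5 (front-loaded): 0.0421, or 126 per 3,000 starters. The risk seen from Visit 1 is 6.8%.

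A material effect needs a real lag and, in addition, either a raised early hazard or person-time counted from first dose.

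**The case for a change.** The best argument for a change is that the natural reading is nowhere written down. With about 40 sites and 80 or more investigators (Section 3.3), a uniform interpretation is not guaranteed. Consecutive enrolment covers patients who meet the inclusion criteria, not consecutive first prescriptions. Section 3.2 discusses several biases but not selection between first dose and entry. The drug was on the market before sites opened, and a clarifying amendment would be cheap.

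Part of this stands. No section equates Visit 1 with the first dose or sets a maximum interval, and late enrolment is not expressly forbidden. The eCRF (Attachment 1) and the separate TSAP were not available, so it cannot be confirmed that a first-dose date is captured, although the flow chart does record Pradaxa administration status at baseline.

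The rest is weaker. Patients already on drug before a site opened are those the first exclusion most naturally removes, and Section 3.1 speaks only of monitoring their adverse event reports, not of enrolling them. The differing anchors are not separate evidence of a defect, because they coincide once treatment starts at Visit 1. Section 5.1.2's requirement of more than 12 weeks on drug sits awkwardly with a visit allowed at week 10, but that is so even at zero lag and is a different matter.

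**Conclusion.** The concern does not call for a change. What is missing is a definition of previous exposure and of day 0, and sites and analysts will fill that gap sensibly, because the only workable reading is new users enrolled at or near treatment start and the rest of the protocol fits it. On that reading the criteria do not conflict, the early-bleed loss does not arise, and the bias is zero.

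If some sites did enrol late, the moderate cases (a quarter of patients, 2 to 4 weeks) give 3.1% to 7.7% over 12 weeks, and only for events that prevent enrolment. Larger figures require every patient to be late, and the 4-week cases mostly imply time on drug beyond the stated treatment duration. Case (b) also needs a person-time analysis, while Sections 5.2.1 and 7.3.3 describe only descriptive adverse event summaries. Cases (c) and (d, front-loaded) need an early hazard that the documents do not give.

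This rests on two assumptions: that sites follow the natural reading, and that nothing in the eCRF or TSAP contradicts it. For a single-arm surveillance study with no hypotheses and a sample size set by the regulator, delayed-entry rates or an added sensitivity analysis would bring no gain unless a material lag were found in the data.
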